4.3.1. Subject Numbering

Subjects will be assigned a unique Subject Number at Screening for each cohort the subject opts to participate in. When a subject is known to qualify for randomization, the subject number will remain consistent for the duration of the participation in each cohort. GSK will provide the site with a unique set of Subject Numbers in sequential order beginning with the lowest number. Once a subject number is assigned to a subject, it cannot be re-assigned to any other subject during the study

If a subject is prematurely discontinued from the study and a replacement subject is to be recruited, a replacement treatment number will be used to assign the same treatment to the replacement subject.

4.4. Investigational Product and Other Study Treatment Dosage/Administration

Study Treatment		
Product name:	GSK1278863	Placebo
Formulation description:	White to off-white smooth ointment	White to off-white smooth ointment
Dosage form:	Ointment	Ointment
Unit dose strength(s)/Dosage level(s):	0.05%w/w, 0.1%w/w, 0.5%w/w, 1.0%w/w	Placebo
Route/Administration/Duration:	Topical	Topical
Dosing instructions:	See Section 11 for Dosage and Administration Instructions	See Section 11 for Dosage and Administration Instructions
Device:	Part A: Amber Bottle or White Tube Part B: White Tube	Part A: Amber Bottle or White Tube Part B: White Tube
Manufacturer/source of procurement:	Part A: GlaxoSmithKline Part B: DPT Laboratories, Ltd./GlaxoSmithKline	Part A: GlaxoSmithKline Part B: DPT Laboratories, Ltd./GlaxoSmithKline

4.5. Dose Adjustment/Stopping Criteria

This protocol allows some alteration from the outlined dosing schedule, but the predicted maximum exposure will not exceed systemic exposure to a 15mg oral dose. Modeling currently predicts that the highest dose levels will achieve exposures at or below a 10mg oral dose.

The dosing schedule may also be adjusted to expand a dosing cohort to further evaluate safety and/or pharmacokinetic findings at a given dose level, or to add cohorts to evaluate up to sufficient additional dose levels. The study procedures for these additional subject(s) or cohort(s) will be the same as that described for other study subjects.

These dose adjustments may involve either an increase or a decrease in the planned dose, but all doses will be selected so as not to exceed mean a systemic exposure equivalent to a 15mg oral dose.

4.5.1. Dose Adjustment/Stopping Safety Criteria

An individual patient will be withdrawn from the study at the discretion of the Investigator and the study team. In the event one or more patients are withdrawn, additional patients may be enrolled to ensure an adequate number of patients complete each cohort.

4.5.1.1. Hemoglobin Stopping Criteria

A patient that experiences an absolute increase in hemoglobin of 1.5g/dL above their baseline level at any time will be withdrawn from the study.

Should hemoglobin values achieve the above set criteria, additional samples may be collected every 2-3 days and appropriate procedures (venesection or erythrocytapheresis) may be considered and implemented at the discretion of the investigator until the laboratory result returns to the patient's normal range.

4.5.1.2. Liver Chemistry Stopping Criteria

Liver chemistry threshold stopping criteria have been designed to assure subject safety and to evaluate liver event etiology (in alignment with the FDA premarketing clinical liver safety guidance).

Study treatment will be stopped for a subject if the following liver chemistry stopping criteria is met:

- ALT \geq 3xULN

Refer to Section 14, Liver Chemistry Follow-up Procedures, for details of the required assessments if a subject meets the above criteria.

4.5.1.3. QTc Withdrawal Criteria

Healthy Volunteers (Part A, Cohort 1)

A subject that meets criteria below will be withdrawn from the study. The QT correction formula used to determine discontinuation should be the same one used throughout the study.

- QTc $>$ 500msec

Withdrawal decisions are to be based on an average QTc value of triplicate ECGs. If an ECG demonstrates a prolonged QT interval, obtain 2 more ECGs over a brief period, and then use the averaged QTc values of the 3 ECGs to determine whether the subject should be discontinued from the study.

DFU Patients (Part A Cohorts 2 through Final Cohort, Part B All Cohorts)

A subject who meets the criteria below will be withdrawn from the study. The QT correction formula used to determine discontinuation should be the same one used throughout the study.

- QTc $>$ 530msec or uncorrected QT $>$ 600msec
- If subject has underlying bundle branch block then the QTc withdrawal criteria depends on the baseline value:

Baseline QTc value with underlying bundle branch block)	QTc withdrawal criteria
≤500msec	>530msec
≤530 msec	≥550msec

Withdrawal decisions are to be based on an average QTc value of triplicate ECGs. If an ECG demonstrates a prolonged QT interval, obtain 2 more ECGs over a brief period, and then use the averaged QTc values of the 3 ECGs to determine whether the subject should be discontinued from the study.

4.5.1.4. Other Dose Adjustment/Stopping Safety Criteria

- Any other occurrence that raises significant safety concern in the mind of the investigator.
- Any patient who has an increase from baseline in total wound area > 20% at any time will be withdrawn from treatment
- Any patient who develops at any time after randomization 3 of the following 6 signs at the study wound site will be withdrawn from treatment: local erythema, edema, pain, pus, local warmth, loss of function
- Diagnosis of cancer, with the exception of squamous cell and basal cell carcinoma (unless in proximity of the wound treated with GSK1278863).

The GSK Medical Monitor must be notified within 24 hours of any subject's withdrawal as a result of safety concerns.

4.6. Time and Events Table

4.6.1. Time and Events Table Part A

Study Population	Procedure	Screening ¹ (HVT: -28 to -1 days; DFU: -28 to -14 days prior to Day 1)	Study Day (each dosing period)										Follow Up		
			Day 1								Day 2	Day 3	Day 4	7-10 days post last dose	28-32 days post last dose
			Pre-dose	0h	0.25h	0.5h	1h	2h	4h	8h	12h	24h	48h	72h	
All Subjects	Check in			X											
	Informed Consent	X													
	Demographics	X													
	Full Physical Exam	X													
	Brief Physical Exam		X									X	X	X	
	Medical/medication/drug/alcohol history	X	X												
	12-lead ECG ²	X	X									X		X	
	Vital signs ³	X	X									X		X	
	Urine pregnancy(women)	X	X											X	
	HIV, Hep B and Hep C ⁴	X													
	Hema/Chem Safety Labs ⁵	X	X									X		X	
	Blood for HIF α Samples (e.g., hepcidin, EPO, VEGF) ⁶		X							X	X ⁶			X	
	Study treatment dosing			X											
	Pharmacokinetic Sampling ⁷		X		X	X	X	X	X	X	X ⁷	X	X	X	

Study Population	Procedure	Screening ¹ (HVT: -28 to -1 days; DFU: -28 to -14 days prior to Day 1)	Study Day (each dosing period)										Follow Up		
			Day 1								Day 2	Day 3	Day 4	7-10 days post last dose	28-32 days post last dose
			Pre-dose	0h	0.25h	0.5h	1h	2h	4h	8h	12h	24h	48h	72h	
			Concomitant Medications	←-----→										X	
Subjects with DFUs ⁹ Only	Adverse Event Review ⁸		←-----→											X	X
	Gene Expression (mRNA) Tissue Samples ¹⁰			X										X	X
	Biomarker fluid samples (e.g., for cytokines, growth factors, and bioburden)			X										X	X
	Physical Characteristics (e.g., photos and wound measurement post-debridement, volume)		X	X										X	X
	Clinical Characteristics ¹¹	X	X			X	X	X			X	X	X	X	X
	Vascular Perfusion Eligibility Assessments ¹²	X													

1. For subjects with DFUs to be eligible for the study or for entry into more than one cohort in Part A, rate of healing must be assessed in the 14 days prior to Day 1.
2. Single ECGs will be taken at Screening, pre-dose on Day 1, at 48h post-last-dose on Day 3 and at the 7-10 day Follow-up Visit. ECGs should be taken while subject is supine for at least 5 minutes. Additional ECGs may be taken at the discretion of the investigator as needed based on symptoms or ECG findings.
3. Assessment of vital signs (including blood pressure and heart rate) will be performed at Screening and pre-dose on Day 1 and at the 48h post-last-dose on Day 3, and at the Follow-up Visits. Vital signs should be performed after resting in a supine or semi-supine position for at least 5 minutes.
4. HIV, Hep B and Hep C are only assessed in the Healthy Volunteer population.
5. Blood samples for safety analyses will be collected fasting at Screening, on Day 1, at 48h post-last-dose on Day 3 and at the 7-10 day Follow-up Visit. Refer to Section [7.2.4](#) for specific laboratory parameters to be tested.
6. Blood samples HIF α activation on Day 1 will be collected at pre-dose, 8 and 10-12 hour window. Refer to Section [7.6](#) for additional details on the collection and processing of these samples.
7. Serial blood samples for the determination of the PK for GSK127886 and metabolites will be collected immediately pre-dose and 0.25, 0.5, 1, 2, 4, 8, 10-12 (once within the 10-12 window for out-patients only)/12 (in-patient subjects only), 24, 48 and 72hrs post-dose. Refer to Section [7.12](#) for details on the collection and processing of PK samples. PK sampling times may be changed based on the observed GSK1278863 PK profile, but the total number of samples will not change.
8. Adverse events are to be collected from first dose through the final Follow-up Visit.
9. These assessments are to be performed only when IP is applied to the ulcer not to the patient's intact skin unless for screening/eligibility purposes.
10. Tissue sample collection at Pre-dose, Day 4 and the 7-10 Follow-up Visit is at the discretion of the PI or designee. Wounds that have healed such that biopsies would be disruptive to the continued healing process are exempt.
11. Clinical characteristic assessments of the DFU begin with Section [7.10](#) and contain instructions for completing the assessments including the irritation/symptom scale as needed. The 12 hr assessment can be done once within the 10-12 window for out-patients and at 12 hrs for in-patient subjects. Assessments are recorded in the eCRF
12. See Item [7](#) in the Inclusion Criteria – DFU Subjects for acceptable perfusion parameters. Only 1 test of the 4 (TcPO₂, ABI/TcPO₂, toe pressure, Doppler ultrasound) is required for eligibility.

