1.4. Study Design Strategy

This first-time-in-human study of the topical formulation of GSK1278863 is designed as an initial exploration of the safety, tolerability, pharmacokinetic and pharmacodynamic effects. The study will be performed in a cohort of healthy volunteers and then in diabetics, including application both to healthy, intact skin, as well as to diabetic foot ulcers directly. This study proposes to move rapidly into diabetic patients with foot ulcers, as no equivalent model for this disorder exists to understand kinetics and tolerability of the compound. However, to provide some limited understanding of tolerability and kinetics, the study has been designed to gain initial information related to these parameters in healthy individuals with at least two doses of medication prior to entry into the diabetic cohorts. Furthermore, the first diabetic cohort will have the compound applied to intact skin to gauge tolerability in this patient population and to compare PK with that of healthy individuals. Subsequently, the same cohort of diabetic subjects will also receive equivalent dose(s) applied directly to the foot ulcer. A treatment period of two weeks was selected for the repeat dosing segment of the study to permit initial assessment of healing rate and biomarker analyses that are important to inform decisions related to progression of the compound for the indication ([Figure 1](#)).

Figure 1 Study Design/Schematic

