The first cohort of subjects will be healthy volunteers. The starting dose in this cohort will be 0.1% GSK1278863 petrolatum ointment at 25mg/cm² to a 12cm² section of intact skin (300mg total mass of the formulation) on the foot, which will deliver 300 μ g GSK1278863. The site of application will be covered with an occlusive dressing. The dosing vehicle will be removed from the skin by washing at 22.5 hours (Note: For practical reasons, a dosing period of approximately 22.5 hours will be followed for both the single and repeat dosing parts of this study. This allows for subject hygiene and dehydration of the skin prior to reapplication when necessary and will allow consistency between the SD and RD portion of this protocol). The second dose will be 10-fold greater, or a 3000 μ g GSK1278863 dose achieved by using 300mg of the 1% petrolatum ointment formulation. This will be applied to a different 12cm² section of intact skin on the lower limb in the same cohort of healthy volunteers following at least a 10 day washout period. Including a cohort of healthy volunteers allows for determination of the irritation potential of the formulation on intact skin before introducing the study drug to patients. Additionally, this will provide a baseline of GSK1278863 absorption kinetics in healthy skin. As petrolatum formulations have been on the market with numerous drugs, a low potential for irritation is expected in humans.

Diabetics with DFU no larger than 16cm² will be the second cohort of the study and diabetic patients will be used for the remainder of the dose escalation cohorts. Therefore, the largest anticipated amount of petrolatum ointment to be applied to a study wound is 300mg. In general, doses will be escalated by applying the same amount of ointment (25mg/cm²) using a higher percentage ointment. However, if the need arises based on emergent data, doses may be escalated by increasing the amount of ointment applied per cm² skin/wound diameter (i.e., greater than 25mg/cm²).

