4.2.1.4. Cohort 2 (Part A)

Cohort 2 will enroll DFU subjects who fulfill screening criteria. Subjects will be randomized to receive a single application of GSK1278863 or placebo in two dosing periods. The two dosing periods are intended to provide a 'within patient' comparison of PK between application to intact skin and to DFU. The first application will be made on intact skin, followed by a 10-day washout period. Blood for serial PK sampling will be collected out to 72 hours post-dose. After review of safety, tolerability and PK data, these subjects will then receive an application of the same dose directly to the DFU.

Subjects will come in to the clinic fasting early in the morning of Day 1 of each dosing period and will follow the same schedule as Cohort 1, with the exception that the first application will be on intact skin, and the application in the second dosing period will be directly to the DFU. See Section [4.6.1](#) for detailed timing of assessments and sampling.

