4.2.1.5. Cohorts 3 and 4 (Part A)

Cohorts 3 and 4 will enroll DFU subjects who fulfill screening criteria. Subjects will be randomized to receive either GSK1278863 or placebo. Each cohort will evaluate a new dose of GSK1278863, with applications made directly to the DFU. If subjects are re-enrolling from a previous cohort, they must complete the second Follow-up visit (Day 28-32 post last dose) and therefore the 14 day Run-in period may begin 14 days prior to this visit. If Cohort 4 is the final cohort, subjects will also receive application to intact skin.

Subjects in Cohort 3 will come in to the clinic fasting early in the morning of Day 1 and will follow the assessments as outlined in Section [4.6.1](#).

Cohort 4, or the final cohort if optional cohorts are enrolled, will have 2 dosing periods (10 day washout between periods), with GSK1278863 applied directly to the DFU in dosing period one and followed by application to intact skin in the second dosing period. Subjects will follow the same schedule as for Cohorts 1 and 2. See Section [4.6.1](#) for detailed timing of assessments and sampling.

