7.3.1. Part A

Blood samples for HIF α , (e.g., VEGF, EPO). All Cohorts
Biomarker Samples (e.g., for cytokines and bioburden) DFU subjects only
Gene Expression (mRNA) Tissue Samples DFU subjects only
Physical Indicators (e.g., photos and wound measurement) DFU subjects only
Clinical Indicators DFU subjects only

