7.10.3. Irritation Symptom Assessment

An irritation symptom assessment may be completed in both Part A and Part B of the study if ulcer assessments suggest that erythema and/or swelling are present.

Irritation Symptom Scale

Skin Irritation Scale:

Is infection present: Y / N

Erythema:

Score _____

Very slight erythema (barely perceptible) =1

Well-defined erythema = 2

Moderate to severe erythema = 3

Severe erythema[Severe erythema (beet redness) to slight eschar formation]= 4

Swelling/Edema:

Score _____

Very slight edema (barely perceptible) =1

Slight edema (edges are well defined by definite raising) = 2

Moderate (rasing approximately 1 millimeter) = 3

Severe edema (raising more than 1 millimeter and extending beyond the area of exposure = 4

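### Irritation on intact skin is a stated reason for Cohort 1, yet no intact-skin application in Part A has a route to an irritation score

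*Protocol*

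**What the plan says.** **Purpose.** Protocol Section 1.4.1.1 gives two reasons for enrolling healthy volunteers. The first is that this "allows for determination of the irritation potential of the formulation on intact skin before introducing the study drug to patients". The second is PK: "Additionally, this will provide a baseline of GSK1278863 absorption kinetics in healthy skin". Section 1.4 then says that "the first diabetic cohort will have the compound applied to intact skin to gauge tolerability in this patient population", and the same sentence adds a PK comparison with healthy individuals. Section 4.2.1.4 describes Cohort 2's two periods as a within-patient "comparison of PK between application to intact skin and to DFU". Tolerability is part of the first primary objective (Section 2.1).

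**Instrument.** The only irritation scale in either document is the erythema and edema scale in Section 7.10.3, graded 1 to 4. That section says it "may be completed in both Part A and Part B of the study if ulcer assessments suggest that erythema and/or swelling are present". The triggering assessment in Section 7.10.2 is made at the study ulcer.

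**Schedule.** In Section 4.6.1 the scale appears only in the footnote to the Clinical Characteristics row. That row lies in the block for subjects with DFUs only. Footnote 9 to that block reads: "These assessments are to be performed only when IP is applied to the ulcer not to the patient's intact skin unless for screening/eligibility purposes". Section 7.3.1 agrees: "Clinical Indicators DFU subjects only".

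**SAP.** Section 10 and the safety display list (Section 14.1.2) contain no irritation output.

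**The concern.** A stated purpose and the assessment schedule do not meet. Cohort 1 is meant to show whether the ointment irritates intact skin before patients are exposed, and Cohort 2 begins on intact skin to check tolerability in diabetics. A site that follows the schedule exactly completes the irritation scale in neither setting.

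Tolerability also carries weight in decisions. Section 4.2.1.2 makes the second Cohort 1 dose conditional on the first having been well tolerated. Section 4.2.1.6 says that dose selection will use safety and tolerability data where systemic exposure does not permit predictions. If low-grade erythema or edema under the occlusive dressing is not systematically looked for and graded, a report of no irritation on intact skin would partly reflect what was recorded rather than what occurred.

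**Working it through.** There is no power or sample-size figure to reproduce; Section 6.2.1 states that there is no formal calculation. The check is a cross-reading followed by a count.

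**Step 1: is there a route to an irritation score?**

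| Application | Stated purpose | Route to the 7.10.3 scale |
|---|---|---|
| Cohort 1, both periods (intact) | Irritation potential and absorption kinetics (1.4.1.1) | None: the row is for DFU subjects only (4.6.1, 7.3.1) |
| Cohort 2, Period 1 (intact) | Tolerability and PK (1.4, 4.2.1.4) | None: footnote 9 |
| Final cohort, Period 2 (intact) | PK linearity and wound-versus-intact comparison (1.4.1.1, 4.2.1.6) | None: footnote 9 |
| Cohort 2 Period 2, Cohort 3, final cohort Period 1 (wound) | PK, safety, PD | Optional, if erythema or swelling is seen at the ulcer |

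Two separate rules produce the gap. Footnote 9 speaks of the patient's intact skin and does not by itself exclude healthy volunteers. The DFU-only block and Section 7.3.1 do that.

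**Step 2: count the applications.** Inputs are 8 subjects per Part A cohort, 6 active and 2 placebo (Section 6.2.1); treatment area by period (Table 2); no optional cohorts; and every subject completing every period.

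- Cohort 1, intact: 8 × 2 = 16 (12 active, 4 vehicle).
- Cohort 2 Period 1, intact: 8 (6 active, 2 vehicle).
- Intact-skin applications planned before ulcer dosing: 16 + 8 = **24** (18 active, 6 vehicle). Number with a route to an irritation score: **0**.
- Final cohort Period 2, intact: 8 (6 active, 2 vehicle), also with no route, but given after the wound period.
- All intact-skin applications: 24 + 8 = 32. Wound applications: 8 + 8 + 8 = 24. Total: 56.

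For Cohort 2 the order is by period within subject. Section 4.2 allows staggered enrolment, so one subject's wound dose could precede another's intact-skin dose by calendar date.

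**Step 3: what is still captured on intact skin?**

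- AEs, each graded mild, moderate or severe (Section 12.7.1). The grades describe interference with everyday activities.
- A brief physical examination that includes the skin (Section 7.2.1). It is not scored and not directed to the application site.
- Nurse and physician observation, named in the primary safety endpoint (Section 3.1).

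**Step 4: does the SAP separate the areas?** SAP Section 7 gives regimens C and E one display label each. Protocol Table 2 applies each of them to both intact skin and wound. As labelled, AE tables by regimen would pool the two areas for those regimens.

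**The case against.** The strongest reply is that intact skin is not left unobserved. Staff observation is part of the primary endpoint, AEs are elicited by questioning at visits (Section 12.5), each AE receives an intensity grade, and the SAP plans a table of AEs by maximum intensity. Regimens A, B and placebo are separate display groups, so a graded comparison of reported reactions between active and vehicle, and between the two Cohort 1 doses, is planned. This stands. A reader might infer that intact-skin tolerability is never assessed, or that no graded comparison is possible; the documents support neither. What remains is that these grades are coarser, are not specific to the site, and exist only if someone records the reaction as an AE.

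There is also a plausible reason for tying the scale to ulcers. Section 12.1 treats expected transient inflammation near the wound as outside the AE definition unless it is more severe than expected, so ulcers need a separate instrument. No such exclusion is given for intact skin in healthy volunteers. The sponsor also expects little irritation, citing rabbit data at up to 2% (Section 1.5.1) and experience with petrolatum products (Section 1.4.1.1). This lowers the stakes but does not supply the determination that Cohort 1 is said to provide.

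Two further inferences should be resisted. The first is that every intact-skin period exists to check irritation before wounds are dosed. The final cohort runs the other way, "with GSK1278863 applied directly to the DFU in dosing period one and followed by application to intact skin in the second dosing period", and that period serves PK. The second is to set 32 of 56 unscored applications against 24 scored ones. The scale is optional and conditional on ulcers too, so an unremarkable ulcer application also gets no score.

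**Conclusion.** The inconsistency is real and limited in scope. The protocol names irritation potential on intact skin as a reason for Cohort 1 and tolerability as a reason for Cohort 2's first application, but its rules keep the only irritation scale away from both. All 24 planned applications in those settings have no route to a score. The final cohort's 8 intact-skin applications share the gap but have no bearing on the pre-wound check.

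The consequence is reduced sensitivity rather than absence of safety data. Low-grade erythema or edema may go unrecorded, and it cannot be compared on an irritation scale between active and vehicle or between 0.3 mg and the second Cohort 1 dose. With 6 active and 2 vehicle per cohort, any such comparison would be descriptive in any case.

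The count assumes 8 per cohort, full completion and no optional cohorts; the protocol calls these sizes approximate. The finding that none has a route to a score does not depend on those numbers.

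**What to change.** Reconcile protocol Sections 1.4 and 1.4.1.1 with Sections 4.6.1, 7.3.1 and 7.10.3:

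1. Take the irritation score out of the DFU-only block in 4.6.1, and limit footnote 9 to the wound-specific assessments (wound measurement, fluid, tissue, ulcer characteristics).
2. Apply the existing erythema and edema scale, with an added grade for none, to the application site, at minimum in Cohort 1 and Cohort 2 Period 1. Use visits already in the schedule: the 24 h visit (1.5 h after wash-off at 22.5 h, since 24 − 22.5 = 1.5), 48 h, 72 h and the 7-10 day follow-up. That follow-up is timed from the last dose, so it comes after the final period only.
3. In the SAP, add one safety table of worst erythema and worst edema grade by regimen and application area (intact or wound).

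The cost is about a minute per existing visit, one short eCRF page and one table, with no new visit or invasive procedure.

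If the sponsor prefers not to score intact skin, the protocol should say that irritation there is judged from AEs, examination and observation only. The SAP reports that the indication was terminated and that Part A data had already been used to settle Part B. If Part A can no longer be changed, the SAP can still split AE displays for regimens C and E by application area, and the report can state the limitation.
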